**Statistical Analysis Plan**

**Sponsor:** Island Pharmaceuticals Ltd  
**Protocol Number:** ISLA101-P01-CT001

**6.1 Subject Disposition and Analysis Sets**

Summary tables will be based on the Safety Population.

The number and percentage of randomized subjects, subjects completing or discontinuing from the study as well as the primary reason for discontinuation will be presented by treatment group and for all subjects overall in the subject disposition table. The denominator for the reason for discontinuation from the study percentage calculations will be the number of subjects that discontinued from the study.

All subject disposition information (as described in Section 4.4.1) will be listed together with the date that the subjects provided informed consent and the date/time of the first study drug administration in the subject disposition listing.

The number of subjects included in the analysis populations defined in Section 3 will be summarized along with the reasons for exclusion from any analysis population by treatment group and for all subjects overall using frequencies and percentages.

In addition, the inclusion/exclusion of each subject into/from each of the defined analysis set will be listed.

The randomization information (where applicable) including the randomized treatment group will be listed.

**6.2 Protocol Deviations and Eligibility**

Summary tables will be based on the Safety Population.

The number and percentage of subjects with at least one protocol deviation, at least one major protocol deviation, and at least one minor protocol deviation, as well as the number and percentage of subjects with a deviation in each of the deviation categories will be presented by treatment groups in the protocol deviation table. Subjects will be counted once per category, but all deviations will be counted.

All protocol deviation information and all eligibility data will be listed.

**6.3 Demographic**

Summary tables will be based on the Safety Population.

Demographic data (as described in Section 4.4.3) will be summarized and presented by treatment group and for all subjects overall in the demography table. The homogeneity between treatments will be assessed based on the descriptive statistics only.

All collected and derived demographic data will be listed.

**6.4 Baseline Subject Characteristics**

Summary tables will be based on the Safety Population.

Baseline subject characteristics data (as described in Section 4.4.4) will be summarized and presented by treatment groups and for all subjects overall in the baseline characteristics table.

The vital sign parameters will be listed as part of the vital signs listing.

The listings of alcohol breath test results, serology test results, pregnancy test results and urine drug test results will include all available results (collected at scheduled and unscheduled visits) in the clinical database.

**6.5 Medical and Surgical History**

Summary tables will be based on the Safety Population.

## Statistical Analysis Plan

**Sponsor:** Island Pharmaceuticals Ltd  
**Protocol Number:** ISLA101-P01-CT001

Medical and surgical history conditions will be summarized by SOC and by PT within SOC by treatment group and for all subjects overall. Within each category, the number of subjects who experienced a condition (frequency and percentage) and the actual number of events (frequency only) will be presented by treatment group and for all subjects overall. Subjects who experienced the same condition on more than one occasion (based on the specific category) will only be counted once in each relevant category (SOC and PT), but all conditions will be included in the event frequencies. System organ class terms will be sorted alphabetically, and preferred terms will be sorted alphabetically within SOCs in the table.

In addition to the coded terms, the number of subjects with at least one medical and surgical history condition and the total number of events will be presented.

All information that was collected as well as the coded MedDRA terms will be included in the listing. Partial dates will not be imputed.

### 6.6 Prior and Concomitant Medication

Summary of concomitant medication table will be based on the Safety Population.

Concomitant medications will be summarized by WHO-DD ATC Level 2 term and preferred medication name. Within each ATC term and preferred name, the number of subjects who used the medication (frequency and percentage) will be presented. Subjects who used the same medication on multiple occasions will only be counted once. ATC terms and preferred names with ATC term will be sorted alphabetically.

In addition to the summaries by the WHO-DD terms, the number of subjects who used at least one concomitant medication during the study will be presented.

All information as well as the WHO-DD terms, will be included in the relevant prior and concomitant medication listings. Furthermore, the relative medication starts, and end days (relative to the first study drug administration) will be presented where complete medication start and end dates are available.

### 6.7 Efficacy Analyses

Not applicable for this study.

### 6.8 Safety Analyses

Statistical methods for the safety analyses will be descriptive in nature and no formal statistical comparisons will be made. Endpoints will be summarized by the treatment group based on the methods described in Section 5.1.

Safety endpoints will be analyzed based on the Safety Population according to the actual treatment received.

All listings will be presented by treatment group.

#### 6.8.1 Exposure to Study Drug

All collected study drug administration data (as described in section 4.1.1) will be listed.

#### 6.8.2 Adverse Events

All tables will present the number of subjects who experienced an AE (count and percentage) and the actual number of AEs (count only) within each specific category by treatment group. Subjects who experienced multiple AEs will only be counted once in each relevant category (high-level summary, SOC, PT, severity rating or relationship to study drug category), but all events will be included in the event counts. Percentages will be based on the number of subjects in the Safety Population. Tables will only include treatment-emergent events.

## Statistical Analysis Plan

**Sponsor:** Island Pharmaceuticals Ltd  
**Protocol Number:** ISLA101-P01-CT001

The overall summary of TEAEs table will present the total number of subjects who experienced a TEAE and the total number of TEAEs in each of the following categories:

- At least one TEAE.
- At least one serious TEAE.
- At least one severe TEAE.
- At least one treatment-related TEAE.
- At least one TEAE leading to study discontinuation.
- At least one TEAE leading to study drug discontinuation.

The incidence of TEAEs table will include the number and percentage of subjects who experienced at least one TEAE and the corresponding number of events, and furthermore summarize the TEAE data by SOC and preferred term (PT) within SOCs. SOC/PT terms will be sorted alphabetically.

The incidence of serious TEAE table will include the number and percentage of subjects who experienced at least one serious TEAE and the corresponding number of events, and furthermore summarize the serious TEAE data by SOC and preferred term within SOCs. SOC/PT terms will be sorted alphabetically.

The incidence of treatment-related TEAEs table will include the number and percentage of subjects who experienced at least one treatment-related TEAE and the corresponding number of events, and furthermore summarize the treatment-related TEAE data by SOC and PT within SOCs. SOC/PT terms will be sorted alphabetically.

The incidence of TEAEs by severity rating table will include the number and percentage of subjects who experienced at least one TEAE, at least one TEAE within each severity rating ('Mild', 'Moderate', 'Severe') and the corresponding number of events for each severity rating. In addition, the TEAE data will be summarized by SOC, PT within SOCs, and severity rating within SOC and PT. SOC/PT terms will be sorted alphabetically, and severity ratings will be sorted in increasing order of severity (Mild to Severe) within SOCs and PTs in the table.

The incidence of TEAEs by relationship to study drug (causality) table will include the number and percentage of subjects who experienced at least one TEAE, at least one TEAE within each relationship to study drug category ('Unrelated', 'Unlikely', 'Possibly', 'Probably', 'Definitely') and the corresponding number of events for each category. In addition, the TEAE data will be summarized by SOC, PT within SOCs, and relationship category within SOC and PT. SOC/PT terms will be sorted alphabetically, and relationship category will be sorted from the least to the strongest relationship to study drug (Unrelated to Definitely) within SOCs and PTs in the table.

The incidence of TEAEs leading to study drug discontinuation will include the number of subjects who experienced at least one TEAE that lead to study drug discontinuation and the corresponding number of events, and furthermore summarize the TEAE data by SOC and preferred term within SOCs. SOC/PT terms will be sorted alphabetically.

The incidence of TEAEs leading to study discontinuation will include the number of subjects who experienced at least one TEAE that lead to study discontinuation and the corresponding number of events, and furthermore summarize the TEAE data by SOC and preferred term within SOCs. SOC/PT terms will be sorted alphabetically.

The listing of AEs will include all AE data in the clinical database. The listing will present all the information (fields) collected on the 'Adverse Event' eCRF, as well as the SOC and preferred terms obtained from the MedDRA dictionary. In addition, the AE start and end days (relative to the first study drug administration) and a flag indicating whether the AE was treatment emergent will be presented. Non-TEAEs will not be assigned to any treatment. If the AE was ongoing at the end of the study,

## Statistical Analysis Plan

**Sponsor:** Island Pharmaceuticals Ltd  
**Protocol Number:** ISLA101-P01-CT001

'Ongoing' will be presented under the 'End Date Time/Study Day' heading. Partial dates/times will be presented as described in Section 5.1.4.

The subsets of SAEs, treatment-related AEs, AEs leading to the discontinuation of study drug will be listed separately and will include all the information presented in the main AE listing.

### 6.8.3 Laboratory Parameters

The laboratory parameters described in Section 4.1.3 will be summarized and listed.

The summary tables of hematology, coagulation and biochemistry results will present summary statistics for each laboratory parameter within the specific test panel by treatment group. For each parameter, summaries will be presented for the baseline and each scheduled post-baseline visit. In addition, summaries will be presented for the change from baseline values at each scheduled post-baseline visit. Refer to Section 4.1.3 for the handling of character results.

The summary of hematology, coagulation, and biochemistry shift tables will present summaries for the shifts in the result classifications ('Normal', 'Low', 'High') from the baseline to each of the scheduled post-baseline visit for each parameter with a defined reference range, within the specific test panel.

The listings of hematology, coagulation and biochemistry data will include all laboratory data (collected at scheduled and unscheduled visits) in the clinical database. The listings will present all the information (fields) that is available in the laboratory dataset. In addition, the observation that was used as the baseline records (values) for each parameter will be flagged, the change from baseline value and the derived result classification (based on the normal ranges where applicable) at each post-baseline visit will be presented.

The summary of urinalysis table will present the number and percentage of subjects for each of the result classifications (Normal, Abnormal NCS and Abnormal CS) for the baseline, each scheduled post-baseline per parameter.

The listing of urinalysis (including microscopy) data will include all laboratory data (collected at scheduled and unscheduled visits) in the clinical database. The listings will present all the information (fields) that is available in the laboratory dataset. In addition, the observation that was used as the baseline record (value) for each parameter will be flagged.

The FSH parameters will be listed as part of the pregnancy listing.

### 6.8.4 Vital Signs

The vital signs parameters described in Section 4.1.4 will be summarized and listed.

The summary tables of vital signs results will present summary statistics for results at the baseline and each scheduled post-baseline visit for each parameter by treatment group. In addition, summaries will be presented for the change from baseline values (baselines) at each scheduled post-baseline visit.

The listings of vital signs results will include all data (collected at scheduled and unscheduled visits) in the clinical database. The observations that were used as the baseline records for each parameter will be flagged and the change from baseline values at each post-baseline visit will be presented. Height, weight, derived BMI and BSA will be listed only.

### 6.8.5 12-lead ECG Evaluations

The 12-lead ECG parameters described in Section 4.1.5 will be summarized and listed.

The summary of ECG results tables will present summary statistics for results at the baseline and each scheduled post-baseline visit for each parameter by treatment group. In addition, summaries will be presented for the change from baseline values at each scheduled post-baseline visit.

**Statistical Analysis Plan**

**Sponsor:** Island Pharmaceuticals Ltd  
**Protocol Number:** ISLA101-P01-CT001

The summary of ECG overall assessment table will present summaries for the baseline and each scheduled post-baseline visit for the overall result (Normal, Abnormal not clinically significant and Abnormal clinically significant).

If multiple tracings are conducted as part of one assessment, the mean of the three tracings per parameter and the worst clinical interpretation per timepoint will be summarized for each subject. All values will be listed including the mean value per parameter and the worst clinical interpretation. Changes from baseline will be calculated based on the mean values of the triplicates where appropriate.

The listings of ECG results will include all data (collected at scheduled and unscheduled visits) in the clinical database. The observations that were used as the baseline records for each parameter will be flagged and the change from baseline values at each post-baseline visit will be presented.

### **6.8.6 Physical Examination**

The physical examination assessment data described in Section 4.1.6 will be listed.

## **6.9 Pharmacokinetic Analyses**

### **6.9.1 Plasma Concentrations**

The analysis of the PK concentration data will be based on the PK population. The PK analysis will be conducted separately for fenretinide and its metabolism (MPR and oxo-HPR) based on the available concentrations data (data permitting). Results will be presented by treatment group and study visit/time point.

The plasma concentrations data for Fenretinide, MPR and oxo-HPR will be summarized by treatment group and nominal collection time points using the statistics described in Section 5.1.3. Below the lower limit of quantification (BLQ) concentration that occurred prior to the first quantifiable concentration will be set to 0 and treated as missing otherwise, for the calculation of summary statistics. The number of BLQ concentrations per treatment group per time point will be included in the summary of concentrations. Zero values will be excluded from the calculation of the geometric statistics. Missing values will be omitted from the calculation of descriptive statistics.

For Cohort 1 to 3, figures of the individual plasma concentrations vs. actual time profiles (all subjects within a treatment group on the same plot) will be presented on a linear and a log-linear scale for 3 analytes (Fenretinide, MPR and oxo-HPR). For the food effect cohort (Cohort 4 and one of the Cohort 1 to 3), the individual fasting and fed (fasted and fed results for all subjects in separate plots, and plots showing each subject's fasting and fed results in the same plot) plasma concentrations vs. actual time profiles will be presented on linear and log-linear scales. BLQ concentrations that occurred prior to the first quantifiable concentration will be set to 0 and treated as missing otherwise in the linear plots. BLQ concentrations will be set to missing in the log-linear plots.

Mean concentration with error bars for standard deviations vs. nominal time curves will be presented on a linear and log-linear scale for 3 analytes (Fenretinide, MPR and oxo-HPR). All treatment groups will be presented on the same plot. Standard deviation bars will also be presented.

All plasma concentration data will be listed, and the listing will include the calculated elapsed time since the study drug administration in the specific period and the time deviations between the actual and planned sample collection times.

### **6.9.2 Pharmacokinetic Parameters**

The calculated plasma PK parameters described in Section 4.3 will be summarized by treatment group using the statistics described in Section 5.1.3. For  $T_{max}$  and  $T_{1/2}$ , only n, median, minimum, and maximum will be presented. The summary tables will be based on the PK population. The food effect analysis will be analyzed separately based on the food effect cohorts.

**Statistical Analysis Plan**

**Sponsor:** Island Pharmaceuticals Ltd  
**Protocol Number:** ISLA101-P01-CT001

The dose proportionality of fenretinide will be evaluated across Cohort 1 to Cohort 3 under fasted condition based on the  $AUC_{inf}$ ,  $AUC_{last}$  and  $C_{max}$  values, using a power model and a graphical evaluation of the results.

The power model will be used to estimate the slope parameters and the 90% confidence interval (CI) for the slope. The power model is a linear regression model constructed with the natural log transformed dose as the independent variable and the natural log-transformed PK parameter as the dependent variable. The resulting estimated slope ( $\beta$ ) is a measure of dose proportionality, i.e., the relationship is dose proportional when  $\beta=1$ . Associated 90% confidence intervals (CIs) will be presented. Refer to Appendix 1 for the SAS® code that will be used for the analysis. Scatter plots with the power model regression line will be prepared with the natural log-transformed PK parameter results as the values on the y-axis, and the natural log-transformed dose level as the values on the x-axis. The plot will also include the mean parameters values and standard error bars.

The food effect analysis of fenretinide (for cohort 1 to Cohort 3, the highest tolerated dose level cohort will then be evaluated in a fed condition) will be conducted to evaluate the effect of food on fenretinide based on the parameters  $AUC_{inf}$ ,  $AUC_{last}$  and  $C_{max}$ . The natural log-transformed parameters will be analyzed separately using a mixed effect model (data permitting) with the food effect (with and without food) as fixed effect and subjects as a random effect. The geometric means (exponentiated least-squares means) for each food effect and the geometric mean ratio (exponentiated difference between the fed cohort least-square mean as test and the fasted cohort least-squares mean as reference) and the associated 90% confidence interval (CI) will be presented. The geometric mean ratios and the associated confidence intervals will be expressed as percentages. Refer to Appendix 2 for the SAS® code that will be used for the food effect analysis.

The parameters  $AUC_{inf}$ ,  $AUC_{last}$ , and  $C_{max}$  on fenretinide will also be presented graphically by means of box and whisker plots. The results for all treatment groups will be presented on the same plot. The dose-normalized results for each parameter will also be plotted separately.

All parameter results will be listed based on the PK population and any results that may have been excluded from the summary tables will be flagged.

## 7. Changes to the Planned Analyses

### 7.1 Changes to the Analyses Described in the Study Protocol and Protocol Amendments

Not applicable.

### 7.2 Changes from the Statistical Analysis Plan Version x.x to Version x.x

Not applicable.

---

## Statistical Analysis Plan

**Sponsor:** Island Pharmaceuticals Ltd

**Protocol Number:** ISLA101-P01-CT001

**Statistical Analysis Plan**

**Sponsor:** Island Pharmaceuticals Ltd  
**Protocol Number:** ISLA101-P01-CT001

**9. Attachments and Appendices****Appendix 1 Dose Proportionality Analysis SAS® Code**

The following SAS® code will be used for the dose proportionality analysis of fenretinide for the comparison:

```
ODS Output estimates=estimates;
ODS Output diffss=diffs;
PROC MIXED DATA = pk;
  BY param;
  MODEL log_aval = log_dose / ddfm = kr;
  ESTIMATE 'ESTIMATED SLOPE' log_dose 1/cl alpha=0.1;
  ESTIMATE 'INTERCEPT' INTERCEPT 1/cl alpha=0.1;
run;
```

**Statistical Analysis Plan**

**Sponsor:** Island Pharmaceuticals Ltd  
**Protocol Number:** ISLA101-P01-CT001

**Appendix 2 Food Effect Analysis SAS® Code**

The following SAS® code will be used for the food effect analysis:

```
ODS Output lsmeans=lsmeans;
ODS Output diffss=diffss;
PROC MIXED DATA = pk;
  BY param;
  CLASS subjid trt;
  MODEL log_aval = trt / ddfm = kr;
  RANDOM subjid / subject =subjid type=un;
  LSMEANS trt/pdiff=control('Fasted') CL ALPHA=0.1;
RUN;
```

If the unstructured covariance structure results in invalid (i.e., not non-negative definite) results use TYPE=FA0(2) and then TYPE=CSH. If the model still produces invalid results or does not converge use the default covariance structure.

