**2.3 Study Design**

The study is a randomized, double-blind, placebo-controlled single ascending dose (SAD) study of ISLA101 (fenretinide oral capsules) to evaluate safety, tolerability, and pharmacokinetics in healthy human subjects. The study will consist of up to 4 cohorts that will evaluate dose levels of 300 mg/m^2 (fasted), 600 mg/m^2 (fasted), and 900 mg/m^2 (fasted). The highest tolerated dose level cohort will then be evaluated in a fed condition (in a crossover manner). Eight subjects will be enrolled per dose cohort, with 6 subjects receiving active drug and 2 subjects receiving placebo treatment in a blinded manner. Each subject will be allocated to 1 dose level only.

After completing screening activities, eligible subjects will enter the clinical research unit (CRU) on Day -1 for 5 days. Subjects will receive a single dose of study drug in the morning of Day 1 after an overnight fast of approximately 10 hours, followed by additional 4 hours fast after dose for PK sampling. Cohorts 1 through 3 will receive 300 mg/m^2, 600 mg/m^2, and 900 mg/m^2, respectively, under fasted conditions. After the safety review by the independent safety review committee (SRC), the dose level can be escalated to the planned or lower than planned dose level or de-escalated to an intermediate dose level. Decisions to proceed to the next cohort will be made by the Investigator, SRC, and Sponsor based on the safety data from previous cohort(s).

Safety data will be reviewed to identify the cohort that received the highest dose level under fasted condition. The subjects in this cohort will be recalled to evaluate the PK of ISLA101 under fed conditions (8 subjects; Cohort 4). In Cohort 4, subjects will fast for approximately 10 hours overnight and will consume a high-fat, high-calorie meal approximately 30 minutes prior to administration of study drug. No food consumption will be permitted for at least 4 hours post-dose.

For all cohorts, study drug will be taken with up to 240 mL of water. In fasted cohorts, water will be allowed ad libitum except the interval from 1 hour before to 1 hour after the dose. In the fed cohort, water will be allowed ad libitum except the interval from 10 minutes before to 1 hour after dose.

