AUC inf (h*ng/mL)	ISLA101 xxx mg (Fed)	xx	xx.xx	xx.xx	xx.xx	xx.xx
	ISLA101 xxx mg (Fasted)	xx	xx.xx			
AUC last (h*ng/mL)	ISLA101 xxx mg (Fed)	xx	xx.xx	xx.xx	xx.xx	xx.xx
	ISLA101 xxx mg (Fasted)	xx	xx.xx			
C max (ng/mL)	ISLA101 xxx mg (Fed)	xx	xx.xx	xx.xx	xx.xx	xx.xx
	ISLA101 xxx mg (Fasted)	xx	xx.xx			

AUC: Area Under the Curve

An analysis of variance model with fasting status as fixed effect was fitted to the natural log-transformed pharmacokinetic parameters. The geometric least squares mean and geometric mean ratios and confidence intervals were derived by back transforming the point estimates and confidence intervals from the model.

The point estimates and the associated confidence intervals are expressed as percentages.

If it will be concluded that there is a food effect on the rate and extent of absorption of ISLA101 if the point estimates for the AUCinf, AUClast and Cmax ratios lie outside of the range of 80 to 125%.

Program Name: xxx.sas, Creation Date/Time: YYYY-MM-DD HH:MM

Page 1 of x

**Tables, Listings and Figures Shells****Sponsor:** Island Pharmaceuticals, Ltd**Protocol Number:** ISLA101-P01-CT001

**Sponsor:** Island Pharmaceuticals Ltd  
**Protocol:** ISLA101-P01-CT001

Table 14.3.1.1.1 Overall Summary of Adverse Events (Safety Population)

	ISLA101 300 mg Fasted (N=xx) n (%) E	ISLA101 600 mg Fasted (N=xx) n (%) E	ISLA101 900 mg Fasted (N=xx) n (%) E	Pooled Placebo (N=xx) n (%) E
Subjects with at Least One TEAE	xx (xx%) xx	xx (xx%) xx	xx (xx%) xx	xx (xx%) xx
Subjects with at Least One Serious TEAE	xx (xx%) xx	xx (xx%) xx	xx (xx%) xx	xx (xx%) xx
Subjects with at Least One Severe TEAE	xx (xx%) xx	xx (xx%) xx	xx (xx%) xx	xx (xx%) xx
Subjects with at Least One Treatment-Related TEAE	xx (xx%) xx	xx (xx%) xx	xx (xx%) xx	xx (xx%) xx
Subjects with at least one TEAE leading to study discontinuation.	xx (xx%) xx	xx (xx%) xx	xx (xx%) xx	xx (xx%) xx
Subjects with at least one TEAE leading to study drug discontinuation.	xx (xx%) xx	xx (xx%) xx	xx (xx%) xx	xx (xx%) xx

n: Number of subjects, E: Number of adverse events, TEAE: Treatment-emergent adverse event.

Treatment-emergent adverse events are defined as adverse events that commenced or worsened on or after the first study drug administration.

Severe adverse events are defined as adverse events where the event severity is reported as 'Severe'.

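### The Appendix 2 food-effect code does not specify the single random subject effect in SAP 6.9.2, and may report a 90% CI for the fed/fasted ratio that is too short

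*SAP*

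**What the plan says.** SAP 6.9.2 sets out a mixed model for log-transformed AUCinf, AUClast and Cmax "with the food effect (with and without food) as fixed effect and subjects as a random effect". In ordinary usage that means one between-subject variance and one residual variance.

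Appendix 2 gives the SAS code to be used. Its class statement is "CLASS subjid trt", its model statement is "MODEL log_aval = trt / ddfm = kr", and the random statement is "RANDOM subjid / subject =subjid type=un". The comparison is requested with "LSMEANS trt/pdiff=control('Fasted') CL ALPHA=0.1", which yields the 90% CI. A fallback instruction follows: "If the unstructured covariance structure results in invalid (i.e., not non-negative definite) results use TYPE=FA0(2) and then TYPE=CSH". If those also fail or do not converge, the default structure is used.

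The footnote of the Table 14.2.4 shell reads "An analysis of variance model with fasting status as fixed effect was fitted to the natural log-transformed pharmacokinetic parameters". It does not mention a subject term.

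**The concern.** The random statement names the same class variable as the effect and as SUBJECT=, and asks for an unstructured matrix. One random effect per subject has a single variance and needs no covariance structure. An unstructured matrix, and a fallback through FA0(2) and CSH, make sense only when each subject block has two or more random-effect columns. Read literally, the columns here are the levels of subjid, so each subject gets its own between-subject variance.

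Complete pairs might seem to make this harmless, since the fed/fasted contrast lies within subjects. That is true of the estimate. It is not true of the residual variance, which sets the width of the CI. That CI is the main inferential output of the food-effect analysis, and the protocol synopsis says the fed data will support a planned Phase 2 study.

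**Working it through.** **Inputs.** The recalled cohort is one dose cohort, "with 6 subjects receiving active drug and 2 subjects receiving placebo treatment in a blinded manner" (SAP 2.3). The PK population is restricted to subjects who received ISLA101 (SAP 3.2). That gives six fed/fasted pairs, or 12 observations per parameter. SAP 2.4 reports no formal sample-size calculation, and no within- or between-subject SD appears anywhere. The plan therefore has no figure to reproduce. The SDs below are assumptions on the natural-log scale (within 0.2 to 0.4, between 0.15 to 0.8).

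**Step 1: what the statement specifies on the literal reading.** Each subject block carries six columns. TYPE=UN is then a 6×6 matrix G with 6×7/2 = 21 parameters. Subject *i* has a 1 in column *i* only, so the covariance of that subject's two values is G_ii for every pair of entries, plus σ² on the diagonal. Only the six diagonal elements enter the likelihood; the other 21 − 6 = 15 never do. The fit has six separate subject variances and one residual.

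**Step 2: point estimate, complete pairs.** The GLS estimate is the mean within-subject difference whatever the G_ii are, with variance 2σ²/6. At σ = 0.3 this is 2×0.09/6 = 0.0300, and a direct GLS calculation with unequal G_ii gives the same value. The ratio is unaffected.

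**Step 3: residual variance.** With one common subject variance, whenever the between-subject mean square exceeds the within-subject one, the interval is the paired-t interval on 5 df (t = 2.015). With separate variances bounded at zero, on average 2.4 to 3.1 of the six are estimated as zero. Those subjects' fed-plus-fasted totals are then treated as residual variation. They are the subjects closest to the mean, so they pull σ² down and also raise the df.

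**Step 4: size, six complete pairs.** REML in Python, separate variances against one common variance, Satterthwaite df (taken as equal to Kenward-Roger for this contrast), 2,500 simulated trials per row:

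| SD within / between | Residual variance ÷ true (mean) | Median df | CI half-width ÷ one-variance half-width (mean) | Coverage, separate | Coverage, one variance |
|---|---|---|---|---|---|
| 0.3 / 0.3 | 0.75 | 7.0 | 0.84 | 85.7% | 90.3% |
| 0.3 / 0.6 | 0.80 | 6.1 | 0.86 | 85.2% | 89.2% |

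The Monte Carlo standard error of coverage is about √(0.857×0.143/2500) = 0.7 points. With df held at 5, separate-variance coverage is 87.5% and 86.5%. The interval was shorter than the one-variance interval in 98.8% and 99.9% of trials. Smaller runs of 300 trials with 5 df gave standard-error ratios of 0.905 (SDs 0.25/0.5) and 0.888 (0.4/0.4). A standard error about 10% too small and a half-width about 15% too short agree: 0.90 × 1.895/2.015 ≈ 0.85, where 1.895 is t on 7 df. Over five SD pairs at 600 trials each, the mean half-width was 11% to 16% shorter and coverage was 82% to 87%.

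On the ratio scale, for SDs 0.3/0.6 the one-variance half-width averages 0.331. Around a ratio of 100% that is exp(±0.331), or 72% to 139%. Shortened to about 0.86 × 0.331 = 0.285, it is 75% to 133%.

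**Step 5: incomplete pairs.** SAP 4.3 drops AUCinf from summaries when extrapolation or span fails its limits, and Listing 16.2.6.2 flags results excluded from both summaries and analyses. A subject may then contribute one value, whose weight depends on that subject's G_ii. With SDs 0.25/0.5 and two incomplete pairs (300 trials, 3 df), the standard-error ratio was 0.84 and coverage 83% against 88%. In two such runs the ratio moved by more than 5% in 13% and 15% of trials.

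**Step 6: fallbacks.** FA0(2) and CSH both allow a different variance at each level, so Step 1 still applies. FA0(2) is non-negative definite by construction, so that failure cannot trigger a further move. Only the default structure restores one variance.

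**The case against.** The strongest case is that the premise concerns software behaviour the documents do not settle. Each block contains only one subjid value. If PROC MIXED carried a single column per block, TYPE=UN would be one common variance, which is exactly the model in 6.9.2. SAS was not run, and a simulation that builds in six variances cannot show that SAS fits them. The narrowing also needs variances bounded at zero; without the bound, the interval returns to the paired t on 5 df. And the plan does not stop at TYPE=UN: with at least one variance at zero in essentially every trial, and 15 parameters that the data cannot inform, the fit may be judged invalid and the chain may end at the correct default structure. All of this stands, and it makes the finding conditional. It does not make the code a clear specification of 6.9.2.

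A reader might also infer that the food-effect conclusion will be wrong. The documents do not support that. The only stated criterion, in the Table 14.2.4 footnote, compares the point estimates with 80 to 125%, and complete pairs leave those unchanged. SAP 5.2 declares no hypotheses or decision rules, and the fed PK objective is exploratory.

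Nor does the Table 14.2.4 footnote contradict 6.9.2. It omits the subject effect without denying it.

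Precision is limited too. At 300 trials the Monte Carlo error is nearly 2 points, so the 88.7% coverage seen at SDs 0.25/0.5 is not distinguishable from 90% on its own. The 2,500-trial rows carry the coverage claim. The incomplete-pair figures rest on the small runs only.

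**Conclusion.** The concern holds in conditional form. Appendix 2 does not specify the model described in 6.9.2, and its fallback sequence lets the behaviour of the fits choose between a model with subject-specific variances and the intended one. If the former is reported, then with six complete pairs the ratio is right, the standard error is about 10% too small, and the nominal 90% CI covers roughly 85–88%. With incomplete pairs the ratio can shift as well.

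These sizes rest on assumed SDs, on all subject levels being carried in each block, and on variances bounded at zero. The full fallback chain was not modelled, so they describe the fit with separate variances and not the planned procedure as a whole. It would go too far to say that the reported CI will be too narrow, or that a stated conclusion changes. The consequence is confined to the CI of an exploratory analysis and to the incomplete-pair case. The correction is worth making because it is right under either reading of the software.

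**What to change.** In Appendix 2, replace the random statement with `RANDOM INTERCEPT / SUBJECT=subjid;` (or `RANDOM subjid;`) and delete the UN/FA0(2)/CSH sequence. In the Table 14.2.4 footnote, state that subject is a random effect.

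If output already exists, its covariance-parameter table shows which model was fitted: one subject variance, or one per subject.

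The cost is one line of code and a footnote, with no new data. If separate variances would otherwise have been fitted, the CI becomes slightly wider; if SAS already fits one variance, nothing changes except clarity.
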